Informed Consent: Participants will view a brief video about the purpose, risks, and benefits of the study. They will also be informed that participation is voluntary, and that they can withdraw from the study at any point in time. The researcher will then answer any questions the participant might have about the study and the consent form. Participants will indicate

Research Proposal

their willingness to participate by signing a consent form on Qualtrics (see the ‘obtaining informed consent’ section below for more details). Participants will be able to print a copy of the ICD or will be given a copy by a researcher.

Self-report Questionnaires: Participants will then be seated in front of a computer screen and asked to complete a series of questionnaires (see below for a breakdown of the specific measures).

Interview: One of the researchers (a graduate student in clinical psychology) will use selected modules from the SCID-5 (Structured Clinical Interview for DSM-5) to assess the presence of any of the following DSM-5 mental disorders: alcohol or substance use disorders; bipolar disorder; psychosis; and social anxiety disorder. Suicidal risk will be assessed with the Columbia Suicide Severity Rating Scale (C-SSRS).

Behavioral Approach Task: Participants will be fitted with oculus rift headset and then complete a 3-minute speech on an assigned topic, which will be given while watching the video of an audience filmed with 360°-video that is displayed on the oculus rift. This procedure has been previously used in our prior study (IRB # 2016-08-0025).

Figure 1. A researcher wearing the oculus rift VR headset and standing at the podium

Randomization: Following the baseline assessment, if participants are eligible they will be randomized to one of the two intervention conditions (described below).

Intervention – Session 1 (approximately 1 hour)

Intervention Procedures:

Common Intervention Procedures. All participants will complete two intervention (i.e. exposure) sessions within one week. All exposures will be conducted using the VR equipment with videos of an audience, similar to the BAT described above. The intervention will use a standardized protocol. A similar approach has been used by a several studies investigating experimental behavioral intervention strategies for SAD¹⁸⁻²⁰. See below for protocol details:

Research Proposal

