Personal Report of Public Speaking Anxiety (PRPSA²¹): The PRPSA is a 34 item scale that assesses public speaking anxiety. It has been well validated as an instrument and has empirically derived cutoffs indicated low, moderate, and high public speaking anxiety.

Speech Anxiety Thought Inventory (SATI²²): The SATI is a 23-item scale that assesses cognitions associated with public speaking. It has been well validated as an instrument.

Columbia Suicide Severity Rating Scale (C-SSRS²³): The C-SSRS is an interviewer administered scale assessing suicidal ideation and behavior. It has demonstrated good convergent and divergent validity, and high sensitivity and specificity.

Structured Clinical Interview for DSM-5 (SCID-5²⁴): The SCID-5 is a structured clinical interview used to assess DSM-5 diagnoses.

Demographics: Participants will complete a brief demographic questionnaire including age, gender, ethnicity, etc.

Treatment History: Participants will complete a brief questionnaire asking about current and past psychotherapy and pharmacotherapy.

Liebowitz Social Anxiety Scale (LSAS²⁵): The Liebowitz Social Anxiety Scale is a 24 item scale that separately measures fear and avoidance behaviors concerning social

Research Proposal

interactions and performance situations. It is a commonly used measure of social anxiety, and demonstrates strong psychometric properties.

Subjective Units of Distress (SUDS): Visual Analogue Scales will be used to assess levels of fear, anxiety, self-efficacy, performance, stress, anger, shame, and disgust, before and after each speech.

VR Experiences Questionnaire: A questionnaire assessing the participant's experiences during the VR task.

Autism Spectrum Quotient (AQ-10): A brief 10-item questionnaire assessing a basic likelihood threshold for Autism Spectrum Disorder

Physiological measures

Eye-tracking: Eye tracking data during the orientation and speech (described above) will be collected with the SMI eye tracking hmd upgrade for the oculus rift dk2 system.

Skin Conductance Response: Skin conductance will be collected with the Stens NeXus-4 Wireless Bluetooth Biofeedback system.

Pupil dilation data: Pupil dilation will be assessed using the part of the screen capture data including the eyes of the participants (see below).

Heart Rate: Heart Rate will be measured using the Polar heart rate tracking system.

Other measures

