potential participants will be instructed to complete the prescreen or contact us via email. Individuals that are from the Austin community and express interest in participating will be emailed (see attached recruitment email) an online questionnaire via Qualtrics as described above.

Following the online prescreen participants that may be eligible will be invited to the lab for the baseline assessment.

Following the baseline assessment, those who meet the inclusion and do not meet the exclusion criteria for our study will be invited to participate in the remainder of the study.

f. Obtaining Informed Consent

Before completing the online screening, consent will be obtained via an online form. Because the screening will be conducted over the internet, a waiver of signed consent is being requested.

Upon arrival at the lab, participants will be greeted by a project staff member and asked to view a video presentation describing the purpose and procedures of the study.

Following the video, participants will read the informed consent document on the computer screen (ICD; please see attached) and sign it using a mouse, or their finger (if using an ipad). These ICDs will be stored in Qualtrics online and will not be linked to any of the data collected, they will be stored as an individual, standalone survey. The participants for this study must be capable of understanding the nature of this study as well as the potential risks and benefits. These will be fully explained by the introductory video. The video will also review the ICD, making sure to highlight that the different data that will be collected, and that participation is completely voluntary (the participant is free to withdraw from the study at any point in time with no penalty). Prior to signing the ICD, the experimenter will ask the participant if they have any questions that were not answered by the video or in the form. A copy of the ICD will be provided for the participant. Participants will be able to print a copy of the ICD or request a copy from a researcher.

6. Privacy and Confidentiality

Participants' data will be stored and reported in a de-identified fashion. The rooms in which the face-to-face assessment, computer-based self-report assessments, and intervention will be conducted are private. To facilitate confidentiality of the data, we will utilize computer data entry for all self-report assessments. When participants' complete measures onsite a researcher will always be available.

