Efficacy of an Attention Guidance VR Intervention for Social Anxiety Disorder

Statistical Analysis Plan

Date: 06/20/2021

Identifiers: NCT03683823 Unique Protocol ID: 2018-04-0011

Data Analysis Plan

The primary aims of this study were to 1) examine whether an attention guidance augmentation enhanced VRET compared to VRET alone and 2) test whether changes in gaze behavior following the intervention mediated the effects VRET. To test our primary hypotheses regarding the influence of the intervention on fear of public speaking (PRPSA), we conducted Bayesian multilevel models using the *brms* package version 2.15 (Bürkner, 2018). For aim 1 we examined the interaction between assessment and group predicting the outcome post-treatment and at 1-week-followup. For aim 2, we examined the indirect (i.e., mediating) effect of proportion of fixations to uninterested (socially threatening audience members) at the post-treatment assessment, on the relationship between intervention group and the post-treatment assessment of PRPSA at the 1-week-followup (see Figure 3). To facilitate interpretation of the mediation analysis, we partially standardized the model coefficients after completing the analyses using unstandardized variables following recommendations in the literature regarding indirect effect sizes when X is dichotomous (Hayes & Rockwood, 2017; Preacher & Kelley, 2011). In all models, we included average proportion of fixations to audience members during intervention sessions as a covariate to control for variation in treatment adherence. We completed the same analyses to evaluate our secondary outcome of general social anxiety symptoms measured with the LSAS. As integrity checks on the efficacy of the attention augmentation condition we tested whether there were group differences for average number of fixations on audience members during the intervention trials, as well as whether there were differences in proportion of fixations to uninterested audience members post-intervention and at 1-week follow-up.

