We computed Bayes Factors (BFs) using the Savage-Dickey Density ratio (Wagenmakers et al., 2010) for all models where we set priors using the *hypothesis* function in *brms*. The Savage-Dickey Density ratio was calculated in the current context by dividing the posterior density by the prior density at zero (a null effect). Given that priors exert a large influence on the posterior estimates with small samples sizes, we used BFs to provide a sense of the influence of the priors on the study data rather than using them to provide a measure of confidence in the posterior estimates themselves as they are sometimes used (in *brms* if the *hypothesis* function is directional, it provides the latter estimate rather than the Savage-Dickey Density ratio). A BF equal to one means there is equal support for the null and alternative hypotheses while smaller BFs reflect greater support for the null and larger BFs reflect greater support for the alternative, with commonly accepted guidelines for the magnitude of the support (e.g., 1-3 is anecdotal evidence in favor of the alternative; 1/3-1 is anecdotal evidence in favor of the null).

For each result we report the beta estimates, 95% highest posterior density interval (HDI), and BFs of the model estimated with our original prior. We also provide the range of BFs as well as the sensitivity of the beta estimates based on our sensitivity analyses (see below).

Prior Estimates. We set informative priors based on expected effects that were based on a literature review of brief exposure-based intervention for social anxiety, as well as based on expert review. On a theoretical level, use of priors aligns with the idea that all available data should be used to draw inferences – including data from previous findings (Kruschke & Liddell, 2018). On a more practical level, there is substantial evidence to support the use of informative priors to address the ‘winner’s curse’ – which is where significant effects in an initial study are not subsequently replicated (Altoè et al., 2020). Moreover, Lemoine (2019)

conducted simulation analyses showing that weakly informative priors can regularize results in small samples ($n < 50$), providing a more conservative estimate.

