We largely followed the WAMBS (When to worry and how to Avoid the Misuse of Bayesian Statistics) checklist (Depaoli & van de Schoot, 2017). This checklist provides a step-by-step approach to ensuring that a model estimation procedure is acceptable and that the influence of the priors is well delineated. We tested the sensitivity of the priors by using less informative (smaller effects) parameter estimates as well as uninformative default (flat) priors centered on zero to determine the influence of different priors on the posterior estimates.

Priors for the effect of the intervention on fear of public speaking (PRPSA) were primarily based on a relatively recent study which also used a two-session public speaking exposure model (testing affect labeling as a potential mechanism; Niles et al., 2015). In terms of the efficacy of the augmentation for which there is no previous research, we used a prior that reflected a moderate effect ($\Delta 10$ on PRPSA score). It was impossible to predict whether there would be a greater gain at post-treatment followed by a ‘rebound’ (i.e., regression towards the mean) or whether the gains would continue and we tested the sensitivity of our priors by varying the magnitude of the effects as well as their direction (to a certain degree). We also tested a model with uninformative priors, centered on zero. Similarly, for the LSAS we used previous research to determine the priors. One challenge was that most studies addressing fear of public speaking did not have a clinical sample of socially anxious individuals – we predicted greater severity of social anxiety symptoms in the current study – and so drew from other studies as well (Lazarov et al., 2018). We primarily based our estimates of the efficacy of the intervention using a recently published single-session feasibility VRET study (Lindner et al., 2021). The estimate of the effect of the intervention provided a good starting place to inform our priors – based on the

likelihood that 2 sessions would be more potent, we also used estimates from other longer intervention studies.

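### The aim 1 PRPSA and LSAS comparisons are adjusted for in-session gaze, a post-randomisation variable that the guidance arm is trained to change; the primary fit should leave it out

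*SAP*

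**What the plan says.** The SAP's Data Analysis Plan uses Bayesian multilevel models for PRPSA (primary) and repeats them for LSAS (secondary). Aim 1 is read from an interaction: "For aim 1 we examined the interaction between assessment and group predicting the outcome post-treatment and at 1-week-followup". The gaze covariate is not confined to the mediation aim: "In all models, we included average proportion of fixations to audience members during intervention sessions as a covariate to control for variation in treatment adherence". The same section tests, as an integrity check, whether the arms differ in fixations on the audience during the intervention trials.

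On timing, the protocol (section 4, Visit 1) states: "Following the baseline assessment, if participants are eligible they will be randomized to one of the two intervention conditions". Session 1 follows in the same visit. Under Attention Guidance Condition, only that arm is given a target face and told between speeches how much of the time gaze was on it. Gaze comes from a headset tracker (Measures). The outcomes are questionnaires and need no tracker; for example, "The PRPSA is a 34 item scale that assesses public speaking anxiety".

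On priors, the SAP says "We set informative priors based on expected effects that were based on a literature review of brief exposure-based intervention for social anxiety". For the augmentation, "we used a prior that reflected a moderate effect", given as 10 PRPSA points. It does not give the prior SDs or say which coefficients carry a prior.

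The SAP has no model formula, analysis population, rule for missing gaze, imputation, or aim 1 fit without the covariate.

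**The concern.** Aim 1 asks whether adding attention guidance improves outcome, and randomisation supports that comparison as long as nothing arising after it decides who is included or what is held fixed. In-session gaze does arise after it, and gaze is what the guidance arm is coached to change. Adjusting for it raises two separate issues.

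- **Who is analysed.** A regression cannot use a row whose predictor is missing unless the value is imputed or modelled. Someone with PRPSA and LSAS scores but no usable session tracking could then leave the comparison because of a device result. The trial had already stopped short of its recruitment goals (SAP, Power analysis).
- **What is estimated.** In some model forms, holding gaze fixed removes the part of the treatment effect that works through gaze, which is the mechanism aim 2 proposes.

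**Working it through.** **The plan's own figure.** The only design figure in the SAP is a sample size of 60 from an earlier simulation. Its power, effect and SD are not given, so it can be neither reproduced nor refuted. With a 10-point difference, 30 per arm and a two-sided 5% test, power is 80% at SD 13.8, 73% at SD 15 and 49% at SD 20 (SDs assumed). The point does not depend on the 60, which serves below only as an illustrative size.

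**Step 1: gaze as a main effect.** Write the outcome for participant i at assessment t as

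y_it = a_t + γ·g_i + δ_t·g_i + β·x_i + u_i + e_it,

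with g the arm, x the in-session gaze average and t = 0 at baseline. The change from baseline is

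y_it − y_i0 = (a_t − a_0) + δ_t·g_i + (e_it − e_i0).

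The term β·x_i cancels. With complete outcomes and flat priors, the estimate of δ_t is the difference between arms in mean change, with or without x. Simulation agrees (60 participants, three assessments, guidance raising gaze, all parameters assumed): over 150 trials the largest difference was about 5e-13. In one trial the two interactions were −14.386 and −15.752 (SE 3.417) in both fits, while the group main effect moved from 0.20 to 11.05.

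**Step 2: cost in participants.** If a fraction m have outcomes but no session gaze and are not imputed, interval width scales by 1/√(1 − m). The loss rates and the SD of 13.8 are assumptions.

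| m | N from 60 | Width ratio | Power, SD 13.8 |
|---|---|---|---|
| 0% | 60 | 1.000 | 80.1% |
| 5% | 57 | 1.026 | 78.1% |
| 10% | 54 | 1.054 | 75.9% |
| 20% | 48 | 1.118 | 70.9% |

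**Step 3: people who stop before any speech.** The post-treatment assessment directly follows session 2, so they would usually have only a baseline score. Take 30 per arm, participant SD 12, residual SD 9 and 15% with baseline only (4.5 per arm, leaving 25.5).

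- Dropped: SE = √(2 × 81 × 2/25.5) = 3.56.
- Kept with their baseline record: SE = 3.52 (generalised least squares, known variances).

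Dropping them costs about 1.4%.

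**Step 4: other forms that the SAP's wording allows.** Simulated, all parameters assumed, with part of the effect running through gaze:

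| Form | Effect of adding gaze on the aim 1 contrast |
|---|---|
| Main effect, 20% of follow-up missing | mean absolute shift 0.09 points, maximum 0.33 |
| Main effect, priors of SD 5 on group and interaction terms | mean absolute shift 0.53, maximum 1.22 |
| Gaze crossed with assessment | mean interaction from −14.3 to −10.5 |
| Baseline PRPSA as covariate, group effect at post-treatment | mean from −14.1 to −8.4 |

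In the last two rows x no longer cancels. The contrast shrinks by 3.8/14.3, about 27%, and by 5.7/14.1, about 40%.

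**The case against.** The strongest reply is that nothing in the documents shows anyone was lost. Neither reports missing session gaze. The covariate averages up to 12 speeches, so failed tracking in one speech or one session still leaves a value. The guidance arm's feedback required gaze to be read as sessions ran, and screen capture was kept to check the tracking. Exclusion is inferred from how regression treats a missing predictor, and the posted syntax, which the SAP mentions but which is not available here, may deal with it. This stands. The loss is a possibility of unknown size.

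Four stronger readings are tempting and are not supported:

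- *The term adds nothing to aim 1.* This is exact only for a main effect with complete outcomes and no informative prior on the group main effect. The SAP uses informative priors and gives no formula.
- *Everyone who stops early drops out with full follow-up data.* On the visit schedule, a person who stops before the first speech would usually have a baseline record only. The consent text, "participation is completely voluntary (the participant is free to withdraw from the study at any point in time with no penalty", shows that people may leave, but not that gaze is missing in those with outcomes.
- *A session-1-only average predates most of the feedback.* Six speeches give five breaks per session, so that participant has had five of ten. The average covers less exposure than a completer's, but half of the feedback has been given.
- *Differential loss has biased the result.* Steps 2 and 3 concern precision only; no bias from loss has been shown.

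Adherence is a fair question to examine. It is a different question from the randomised comparison.

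**Conclusion.** The point holds in a conditional form. The documents establish that the aim 1 PRPSA and LSAS models carry a post-randomisation covariate that the guidance arm is meant to change, that no handling of missing gaze is described, and that no aim 1 fit without the covariate is planned.

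The consequence depends on the unstated formula. In the simplest form the covariate brings no gain to the interaction and can only cost participants: about 5% on interval width at an assumed 10% loss and 12% at 20%. Those figures apply only to people with outcomes but no usable session gaze. With informative priors on the group terms the estimate moves modestly, by about half a point on average under the assumed SD of 5. Crossed with assessment, or in a baseline-adjusted contrast, the covariate takes out part of the effect under test, about 27% and 40% in the simulations. Those percentages reflect the assumed strength of the gaze pathway and do not estimate what happened in this trial.

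A reader might infer that the randomised comparison has already been broken; the documents do not show that. In none of the forms examined does the term help the aim 1 contrast, and in some it harms it, so it should not be in the primary fit.

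**What to change.** Make the primary aim 1 fit, for PRPSA and for LSAS, the model without the in-session fixation covariate. Include all randomised participants with any value of the outcome, analysed in the arm assigned. State the model formula and which coefficients carry priors.

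Report the covariate-adjusted fit only as a labelled adherence sensitivity analysis, with its own formula and the number of participants per arm who lack session gaze.

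The cost is one term removed from existing syntax, one refit per outcome and a short count by arm. No new data are needed. The aim 2 mediation models are a separate matter and are not changed by this.

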Priors on the effects of the intervention on proportions of fixations to audience members were not based on previously collected data because there is no literature that clearly delineates expected changes in gaze during public speaking challenges. We chose priors that reflected modest but meaningful effects, indicating changes in gaze behavior substantial enough to have potential implications for treatment outcomes as a causal mechanism. As with the other analyses, we tested several priors reflecting smaller effects as well as an uninformative prior centered on zero.

Power analysis. We did not conduct a power analysis that reflected the sample size for the current pilot study. We had initially conducted a power analysis through a simulation study prior to COVID-19, which indicated a sample size of 60 would be sufficient to detect a meaningful effect for both aims 1 and 2. However, due to COVID-19 enrollment ended before we could meet our recruitment goals. Given that research was necessarily stopped, we decided to rely on the strengths of the Bayesian approach highlighted above to investigate whether it would be worthwhile to conduct a more extensive RCT with a larger sample.

Data and syntax are available at <https://osf.io/un92m/>.

References

Bürkner, P. C. (2018). Advanced Bayesian multilevel modeling with the R package brms. *R Journal*. <https://doi.org/10.32614/rj-2018-017>

Depaoli, S., & van de Schoot, R. (2017). Improving transparency and replication in Bayesian statistics: The WAMBS-checklist. *Psychological Methods*. <https://doi.org/10.1037/met0000065>

Hayes, A. F., & Rockwood, N. J. (2017). Regression-based statistical mediation and moderation analysis in clinical research: Observations, recommendations, and implementation. *Behaviour Research and Therapy*. <https://doi.org/10.1016/j.brat.2016.11.001>

Kruschke, J. K., & Liddell, T. M. (2018). Bayesian data analysis for newcomers. *Psychonomic Bulletin and Review*. <https://doi.org/10.3758/s13423-017-1272-1>

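### The SAP's formula for the Bayes factor and its scale for reading it run in opposite directions

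*SAP*

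**What the plan says.** The relevant text is the paragraph on Bayes factors in the SAP's Data Analysis Plan.

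- **Scope.** Bayes factors come from the Savage-Dickey density ratio "for all models where we set priors". A Bayes factor is reported with the beta and the 95% highest-density interval for each result, and a range of Bayes factors is reported from the sensitivity analyses.
- **Definition.** The ratio was "calculated in the current context by dividing the posterior density by the prior density at zero (a null effect".
- **Direction of reading.** A value of 1 is neutral; beyond that, "smaller BFs reflect greater support for the null and larger BFs reflect greater support for the alternative".
- **Bands.** "1-3 is anecdotal evidence in favor of the alternative; 1/3-1 is anecdotal evidence in favor of the null".
- **Role.** The SAP limits the use of the Bayes factors: "we used BFs to provide a sense of the influence of the priors on the study data", as opposed to measuring confidence in the posterior estimates.

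Neither document mentions a reciprocal or labels the quantity BF01 or BF10. No Bayes factor value is given. For code, the SAP says "Data and syntax are available at" an outside repository, which was not available for this review.

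**The concern.** The definition puts the posterior density in the numerator and evaluates it at the null value. A large ratio therefore means that the data have moved belief towards zero. The reading scale says that a large value means support for an effect. A reader who computes the ratio as defined and reads it as instructed will take evidence for an effect as evidence for the null, and the reverse.

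The ambiguity reaches every result that carries a Bayes factor: wherever priors were set, it covers the primary models for public speaking fear (PRPSA), the mediation analysis, the secondary social anxiety outcome (LSAS) and the integrity checks on gaze. Of the three quantities reported per result, the Bayes factor is the only one to which the SAP attaches a null-versus-alternative reading. If its direction is undefined, the sensitivity range cannot be interpreted either. The SAP is written in the past tense, so values may already have been reported.

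**Working it through.** There is no Bayes factor in the documents to reproduce. The check is therefore algebraic, followed by an illustration.

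**Step 1: what the stated ratio is.** Let H0 be effect = 0, nested in H1, where the effect has the stated prior. Bayes' theorem under H1, evaluated at zero, gives

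p(0 | data) = p(data | 0) × p(0) / p(data | H1).

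Dividing by the prior density p(0):

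p(0 | data) / p(0) = p(data | H0) / p(data | H1) = BF01.

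Values above 1 favour the null and values below 1 favour the alternative. The SAP's scale is that of BF10 = 1/BF01. The two agree only at 1. This step needs no assumption about the priors' spread or the data.

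**Step 2: inputs for an illustration.** From the SAP (Prior Estimates): for the augmentation effect, "we used a prior that reflected a moderate effect", given as 10 PRPSA points; I sign it as a reduction, so the prior mean is m = -10. Assumed, because the documents do not give them: prior SD s = 5 or 10; standard error se = 4, 5, 6, 8 or 10; estimate e = -10 or 0. That makes 2 × 5 × 2 = 20 settings, using a simple normal model.

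Formulas:

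- posterior variance v = 1/(1/s² + 1/se²)
- posterior mean = v × (m/s² + e/se²)
- stated ratio = posterior density at 0 / prior density at 0, which simplifies to [√(s² + se²)/se] × exp{-e²/(2se²) + (e - m)²/(2(s² + se²))}

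**Step 3: two settings in full (s = 5, se = 5).** Here v = 1/(1/25 + 1/25) = 12.5, so the posterior SD is 3.536. The prior density at 0 is exp(-100/50)/(5 × 2.5066) = 0.01080.

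- *Estimate -10.* The posterior is N(-10, 3.536). Its density at 0 is exp(-100/25)/(3.536 × 2.5066) = 0.00207. The ratio is 0.00207/0.01080 = 0.19, and the reciprocal is 5.2. The 95% interval is -10 ± 1.96 × 3.536 = -16.9 to -3.1.
- *Estimate 0.* The posterior is N(-5, 3.536). Its density at 0 is exp(-25/25)/(3.536 × 2.5066) = 0.0415. The ratio is 0.0415/0.01080 = 3.84. The 95% interval is -5 ± 6.93 = -11.9 to 1.9.

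| Estimate | Stated ratio | SAP scale reads it as | What the data say | 95% posterior interval |
|---|---|---|---|---|
| -10 | 0.19 | beyond anecdotal, for the null | effect favoured 5.2 to 1 | -16.9 to -3.1 |
| 0 | 3.84 | beyond anecdotal, for the alternative | null favoured 3.84 to 1 | -11.9 to 1.9 |

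**Step 4: range over the 20 settings.**

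- Estimate -10: from (√41/4) × exp(-100/32) = 0.07 (s = 5, se = 4) to (√200/10) × exp(-100/200) = 0.86 (s = 10, se = 10). The data favour an effect by 14.2 to 1 down to 1.2 to 1, while the scale reads every value as support for the null.
- Estimate 0: from (√125/10) × exp(100/250) = 1.67 (s = 5, se = 10) to (√41/4) × exp(100/82) = 5.42 (s = 5, se = 4). The data favour the null by that factor, while the scale reads every value as support for the alternative.

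**Step 5: check of the identity.** In 24 settings (prior mean -10 or 0; prior SD 5, 10 or 20; standard error 5; estimates 0, -5, -10 and -20), the stated ratio equalled the null-over-alternative ratio of marginal likelihoods, found by numerical integration, to four decimals.

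**The case against.** The strongest reply is that this may be one slip of wording. The direction is given consistently by the general statement and both bands, and only the definitional clause disagrees. If the computed values match the scale, a reader who uses the scale is not misled. Betas and intervals are unaffected, no Bayes factor threshold or decision rule is stated, and the SAP expressly declines to use Bayes factors as a measure of confidence in the estimates. All of this is correct, and it limits the consequences. It does not remove the conflict: the documents cannot show which sentence matches the computation, and the SAP still supplies evidence bands and reports a Bayes factor for each result.

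The remark about directional hypotheses does not rescue the text, because the SAP says that case yields a different quantity instead of the Savage-Dickey ratio.

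Two further points stand in part. First, under Power analysis the SAP says it will "rely on the strengths of the Bayesian approach highlighted above to investigate whether it would be worthwhile to conduct a more extensive RCT". That most naturally refers to the merits argued for informative priors and does not name Bayes factors, so I would not claim that the decision on a larger trial turns on their direction. Second, the illustration shows direction only; that every setting is misread follows from the algebra and is not separate evidence. In the first worked setting the interval beside the Bayes factor would alert a careful reader. In the second, an interval of -11.9 to 1.9 leans towards an effect because of the prior and would give no such warning.

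**Conclusion.** The concern holds. The definition is BF01 and the reading scale is BF10, within one paragraph, with nothing to reconcile them. Followed as written, they reverse the meaning of every Bayes factor other than 1, in every model where priors were set. That conclusion rests on the two statements alone.

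The numerical size in this trial is unknown because no Bayes factor is given. The illustrative ranges (0.07 to 0.86 at an estimate of -10, 1.67 to 5.42 at an estimate of 0) depend on assumed prior SDs, standard errors and estimates; only the 10-point prior effect comes from the SAP. What is shown is a contradiction in the plan, not an inverted result. It needs correcting before any Bayes factor or sensitivity range is interpreted.

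**What to change.** Choose one direction and label it:

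- define BF10 as the prior density at zero divided by the posterior density at zero, and keep the present scale and bands; or
- keep the stated ratio, label it BF01, and reverse the scale and both bands, so that values above 1 favour the null.

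Then check the analysis syntax to see which direction was computed. Take reciprocals only of those reported Bayes factors and sensitivity ranges that do not match the labelled scale; when a range is inverted, its limits also change places.

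The cost is a small wording correction to one paragraph of the SAP, a check of the syntax, and a check of the reported values. No model needs to be refitted.
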